- c. Men who are potentially fertile (not surgically [eg, vasectomy] or congenitally sterile), whose female partners are of childbearing potential, must use contraception for the duration of the study and for 90 days after discontinuation of study drug (because of the possible effects on spermatogenesis). Highly effective methods of

contraception are those with a failure rate of less than 1% per year (eg, female partner's use of hormonal contraceptive [oral, implanted, transdermal, injected], female partner's use of an IUD), and barrier method with spermicide. In addition, male patients may not donate sperm for the duration of the study and for 90 days after discontinuation of study drug.

- d. Body weight ≥ 50 kg.
- e. A sum of ≥ 25 points on the UHDRS-TMS at the screening visit.
- f. Able and willing to provide written informed consent prior to any study related procedure being performed at the screening visit. Patients with a legal guardian should be consented according to local requirements.
- g. Willing to provide a blood sample for genetic analyses (including CAG analysis, CYP2D6 status, S1R polymorphs, genetic long QT syndrome in patients who had QT prolongation following study drug administration or any other genetic analyses related to pridopidine response or HD) at the screening visit.
- h. Willing and able to take oral medication and able to comply with the study specific procedures.
- i. Ambulatory, being able to travel to the study center, and judged by the investigator as likely to be able to continue to travel for the duration of the study.
- j. Availability and willingness of a caregiver, informant or family member to accompany the patient to the clinic at study visits. The suitability of the caregiver should be judged by the investigator.
- k. For patients taking allowed antipsychotic, antidepressant or other psychotropic medication, the dosing of medication must have been kept constant for at least 6 weeks before baseline (visit 2, day -1) and must be kept constant during the study.
- l. Are able to understand the requirements of the study; are willing to comply with the requirements of the study (eg, imaging procedures, all restrictions) and provided their written informed consent to participate in the study.

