- t. Planned medical treatments (excluding dental care) during the study period, which may interfere with the study.
- u. Use of one of the following prohibited drugs, substances, or foods as follows:
 - an investigational drug (new chemical entity) within 6 weeks prior to the first day of study drug administration or within 5 half-lives (whichever is longer)
 - any monoamine oxidase inhibitors within 14 days before the first day of study drug administration
 - any other medications (including over-the-counter [OTC] medications, vitamins, or herbal or nutritional supplements) within 7 days before the first day of study drug administration (except paracetamol/acetaminophen or ibuprofen used occasionally, up to 24 hours before the first day of study drug administration)

- drugs known to significantly inhibit CYP2D6 enzyme drug metabolism within 21 days prior to the first day of study drug administration or within 5 half-lives (whichever is longer) before the first day of study drug administration, or drugs known to significantly induce CYP enzyme drug metabolism within 28 days before the first day of study drug administration
- drugs known to cause significant QT-prolongation such as anti-arrhythmic drugs or antidepressants within 28 days before the first day of study drug administration
- daily consumption of more than 6 units of caffeine and/or xanthine-containing products, within 2 weeks before the first dose of study drug, or not able to refrain from consumption of more than 2 units of caffeine-containing foods or drinks from 48 hours prior to admission visit and discharge. One caffeine unit is contained in the following items: 1 cup of coffee, 2 cans of cola, 1 cup of tea, $\frac{1}{2}$ cup of energy drink (eg, Red Bull) or 3 chocolate bars. Subject should be able to abstain from caffeine intake for 20 hours during any day.
- cigarette smoking (defined as >5 cigarettes per week) or use of other nicotine-containing products (eg, snuff, nicotine patch, nicotine chewing gum, mock cigarettes, or inhalers). Ex-smokers should have ceased smoking at least 6 months before screening.
- any food or drink/beverage containing alcohol, grapefruit or grapefruit juice, apple or orange juice, vegetables from the mustard green family (eg, kale, broccoli, watercress, collard greens, kohlrabi, brussel sprouts, mustard), and charbroiled meats within 7 days before the first day of study drug administration until after the last day of pharmacokinetic sampling.

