- a positive urine drug test or a positive alcohol breath analyzer test at admission visits, or not willing or able to refrain from illicit drugs during the study.

v. Donation or reception of any blood products (eg, plasma, platelets, etc) in the 1 month before the first day of study drug administration, or has made more than 2 donations within the 12 months preceding the first day of study drug administration, or plans to donate during the study or during the 1 months after the last study visit.

w. The subjects cannot participate or successfully complete the study, in the opinion of the investigator, for any of the following reasons:

- The subject is mentally or legally incapacitated, or unable to give consent for any reason.
- The subject is in custody due to an administrative or a legal decision, or under tutelage, or being admitted to a sanitarium or social institution.
- The subject is unable to be contacted in case of emergency.
- The subject is an employee of the site or a relative of an employee at the site.
- Any other reason, at the discretion of the investigator.

Patients with Huntington's disease:

- a. CYP2D6 poor metabolizers
- b. The patient has been previously exposed to ionizing radiation or radioactive substances as a result of clinical research or medical treatment in the past 10 years.
- c. The patient has large scale tattoos, in particular involving the head and neck area.
- d. The patient has a counterindication to having an MRI, including (but not limited to):
 - The presence of metal implants (excluding metal dental crowns) that could affect MRI imaging OR
 - has worked with ferrous metals either as a vocation or hobby (for example sheet metal worker, welder or machinist) in such a way that might have led to unknown indwelling of metal fragments that could cause injury if moved in response to the magnetic fields during the MRI imaging.
- e. The patient suffers from claustrophobia or needle phobia.
- f. The patient has a finding on screening MRI that will, in the opinion of the PI impair the safety of the subject or the scientific integrity of the study.
- g. The patient has a severe motor impairment that might cause artifacts.
- h. The patient has an known coagulation abnormality.
- i. Parts A and 0 only: Individuals who had evidence of only one patent arterial supply to the hand (modified Allen test).

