- p. Patients receiving medications (within the last 6 weeks prior to baseline [visit 2, day -1]) that have been proven to prolong QT interval or who may require such medications during the course of the study such as, but not limited to, non-allowed anti-psychotic medications, tricyclic antidepressants and/or Class I antiarrhythmics.
- q. Patients receiving medications (within the last 6 weeks prior to baseline [visit 2, day -1]) that are metabolized by CYP2D6 and have the potential of reducing seizure threshold.
- r. Creatinine clearance <60 mL/min at screening, calculated using the Cockcroft-Gault equation: $(140 - \text{age}) \times \text{mass (kg)} / 72 \times \text{serum creatinine (mg/dL)}$. It is allowed to repeat the test once, if clinically appropriate.
- s. Any clinically significant, abnormal, screening laboratory result, which in the opinion of the investigator, affects the patients' suitability for the study or puts the patient at risk if he enters the study.
- t. Alcohol and/or drug abuse within the 6 months prior to screening, as defined by [DSM-5 \(American Psychiatric Association 2013\)](#).
- u. Patients with adverse events of suicidal ideation or attempt at any time in the past or as measured by suicide ideation score of ≥ 3 on the C-SSRS (screening version), or patients who answer "Yes" on any of the 5 C-SSRS Suicidal Behavior Items (actual attempt, interrupted attempt, aborted attempt, preparatory acts, or behavior) if the attempt or acts were performed at any time in the past, or patients who, in the opinion of the investigator, present a risk of suicide.
- v. Patients with known intracranial neoplasms, vascular malformations, history of cerebrovascular accident, or intracranial hemorrhage.
- w. Current or history of clinically significant allergy or known hypersensitivity to any ingredients of the study medication [REDACTED]
- x. Treatment with tetrabenazine within 6 weeks of study baseline (visit 2, day -1).
- y. Treatment with any investigational product within 6 weeks of screening prior to the first day of study drug administration or within 5 half-lives (whichever is longer) or

patients planning to participate in another clinical study assessing any investigational product during the study.

z. Use of one of the following prohibited substances, or foods as follows:

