5.3. Prior and Concomitant Medication or Treatment

Medications administered prior to any study drug administration will be recorded as prior medications and medications administered following the first dose and throughout the study will be recorded as concomitant medication. Any prior or concomitant therapy, medication, or procedure a subject has had within 28 days before study drug administration and up to the end of the study period, including follow-up, will be recorded on the CRF. Generic or trade name, indication, dosage, and dosing start and stop times will be recorded. The sponsor will encode all therapy and medication according to the World Health Organization drug dictionary (WHO Drug).

For healthy subjects, other than study drug, no drug is allowed during the study, except for the occasional use of paracetamol/acetaminophen or ibuprofen. Prohibited medication for HD patients is detailed in Section 5.3.1.

At each clinic visit after the screening visit, the investigator will ask subjects whether they have taken any medications (other than study drug), including OTC medications, vitamins, or herbal or nutritional supplements, since the previous visit. Indication, dosage, and start and end dates should be entered on the CRF.

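### The HD eligibility rules do not bar significant CYP2D6 inhibitors as a class, although the healthy-subject rules do and poor metabolisers are excluded from both groups

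*Protocol*

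**What the plan says.** **Healthy subjects.** Criterion u in Protocol Section 4.2 excludes use of "drugs known to significantly inhibit CYP2D6 enzyme drug metabolism within 21 days prior to the first day of study drug administration", extended to 5 half-lives where that is longer. This is stricter than the general rule in the same criterion, which covers other medications, including over-the-counter products, vitamins "or herbal or nutritional supplements) within 7 days before the first day of study drug administration", apart from occasional paracetamol or ibuprofen.

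**HD patients.** Inclusion criterion k in Section 4.1 begins "For patients taking allowed antipsychotic, antidepressant or other psychotropic medication" and requires the dose to be constant for at least 6 weeks before baseline and throughout the study. Section 5.1.1 allows HD patients up to 112.5 mg. On co-medication, Section 5.3 states: "Prohibited medication for HD patients is detailed in Section 5.3.1". That section consists of named-drug lists under six subheadings. In Section 4.2, HD criterion p covers QT-prolonging drugs, "such as, but not limited to, non-allowed anti-psychotic medications, tricyclic antidepressants and/or Class I antiarrhythmics", and criterion q covers drugs "that are metabolized by CYP2D6 and have the potential of reducing seizure threshold".

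**Both groups.** Poor metabolisers are excluded (criterion a in each list). Section 8.1.2 explains that subjects with inactive enzyme have higher exposure and run a greater risk of known adverse events.

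**The concern.** A drug that strongly inhibits CYP2D6 can put a patient with a normal genotype in a position similar to that of a poor metaboliser, and screening genotyping would not reveal it. The protocol guards against this in healthy subjects, who may take almost no other drugs. It has no matching class rule for HD patients, who may remain on psychotropic treatment and whose dose ceiling is higher (112.5 mg against 90 mg).

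What is at stake is chiefly safety. Followed as written, the rules could admit and dose an HD patient whose pridopidine exposure is raised in the way that the poor-metaboliser exclusion is meant to prevent. A secondary matter is comparability, because Section 1.7 includes HD patients to see whether the healthy-subject results are replicated.

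**Working it through.** The plan states no figure on this point. The check is a comparison of the two sets of rules in Protocol Sections 4.1, 4.2 and 5.3.1.

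| Rule | Healthy subjects | HD patients |
|---|---|---|
| CYP2D6 poor metabolisers | Excluded (a) | Excluded (a) |
| Significant CYP2D6 inhibitors | 21 days or 5 half-lives (u) | No class rule |
| Significant CYP inducers | 28 days (u) | No class rule |
| MAO inhibitors | 14 days (u) | No class rule |
| Any other medication | 7 days (u) | No general rule; stable allowed psychotropics continue (inclusion k) |
| QT-prolonging drugs | 28 days (u) | 6 weeks (p) |
| Investigational drugs | 6 weeks or 5 half-lives (u) | 6 weeks or 5 half-lives (y) |
| Maximum dose | 90 mg | 112.5 mg |

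1. **Counterparts.** Healthy criterion u has five drug bullets, with inhibitors and inducers sharing one. Two have an HD exclusion counterpart (p and y). The inhibitor limit has none.
2. **Direction of the HD CYP2D6 wording.** Criterion q concerns drugs that CYP2D6 metabolises and that can lower the seizure threshold. Section 5.3.1.6 gives two grounds: QT prolongation and conversion by CYP2D6 into active metabolites. Both CYP2D6 grounds describe substrates. Neither describes a co-medication that slows pridopidine's own metabolism.
3. **Other routes.** HD criterion z opens "Use of one of the following prohibited substances, or foods as follows"; unlike healthy criterion u, it does not mention drugs. The healthy list ends with a catch-all, "Any other reason, at the discretion of the investigator", which the HD list lacks. The HD prohibited-medication subsections, the HD restrictions in Section 5.2 and the SAP add no inhibitor rule.
4. **Washout.** For healthy subjects the inhibitor washout is at least 21 / 7 = 3 times the general one. For an HD patient on an inhibitor that is not otherwise barred it is 0 days. If that drug is a psychotropic, criterion k in fact requires it to continue unchanged through dosing.
5. **Number exposed.** Section 9.1 plans for up to 4 HD patients, and the cohort is optional. Each receives one dose. The documents label no permitted drug as an inhibitor, so the number affected lies between 0 and 4 and cannot be narrowed.

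**The case against.** The strongest case against is that nobody affected can be identified from the documents. Six named-drug subsections plus the open-ended criterion p may already remove many inhibitors, and finding one that survives needs outside pharmacology. This stands, and it limits the size of the point. It does not close the gap: lists drawn up for other reasons are not a class bar.

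The HD rules also differ from the healthy rules on purpose. Three of the five drug bullets have no HD counterpart, and the creatinine clearance limits differ (90 against 60 mL/min). That is fair, but no visible text explains why this limit was dropped in the group that is allowed co-medication. A reason may sit in redacted parts of Sections 1.5.1, 4.3 or 8.1.2. The HD criteria themselves can be read, so the absence of the bar is not an effect of redaction.

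The poor-metaboliser analogy is imperfect. Section 8.1.2 excludes inactive enzyme, while intermediate metabolisers are only genotyped, so some loss of activity is tolerated. Only strong inhibition matches the stated concern.

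Safeguards exist. Dosing is supervised (Section 5.4). Patients stay seated or supine for an hour after the dose (5.2). QTcF above 450 msec at screening excludes. ECGs are taken before dosing, at about 90 minutes and at about 3.5 hours (7.6), on day 2 and at follow-up (3.14.3.3, 3.14.4). Medication is reviewed the day before dosing (3.14.3.1), and the investigator or sponsor may withdraw a patient at any time (3.12). These reduce the risk, but none instructs the site to exclude a patient on an inhibitor.

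**Conclusion.** The gap is real and worth closing, but modest: a single-dose safety point for at most 4 patients in an optional cohort, with the safeguards above in place. It rests on two assumptions: that at least one significant inhibitor escapes the named lists and criterion p, and that inhibition can be strong enough to resemble inactive enzyme. The documents neither confirm nor exclude either.

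A reader might infer three stronger things that the documents do not support.

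- **That the HD pharmacokinetic summary would be materially distorted.** One inhibited patient among four could shift it, but no effect size is given, so the shift cannot be sized. The summaries are descriptive (Protocol Section 9.6) and include the median, minimum and maximum. Individual parameters are listed (SAP 9.3.2), and HD co-medication is listed (SAP 7.8), so such a patient could be picked out.
- **That the concentration-occupancy model would be biased.** The Emax model in Protocol Section 9.7 uses measured plasma concentration, so raised exposure moves a patient along the curve and does not by itself bias it.
- **That HD patients will receive 112.5 mg while inhibited.** That dose is a ceiling, not the assigned HD dose.

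**What to change.** Add one exclusion to the HD list in Section 4.2 and the synopsis, and a matching subheading in Section 5.3.1: medicines known to inhibit CYP2D6 significantly are prohibited in the 6 weeks before baseline (visit 2, day -1), or for 5 half-lives if that is longer, and for the rest of the study.

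Six weeks matches the existing HD medication rules. It is 6 × 7 = 42 days, or 42 / 21 = 2 times the healthy-subject minimum, so the half-life clause matters only for a half-life above 42 / 5 = 8.4 days.

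The drafting cost is one criterion in two places and one subheading. The real cost is eligibility: a patient on a stable inhibiting psychotropic could not join the optional HD cohort. How many that removes is unknown, because the documents give no co-medication data. The change does not address CYP inducers, so it closes the safety gap but does not make the two groups fully comparable.
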